Mobile learning resources as a tool for improving clinician's ability to break bad news: A pre-post mixed methods pilot study

Version 2.1, 18th March 2019

Sponsors: Imperial College London Funders: Imperial College London Study Coordination Centre: Imperial College London IRAS Project ID: 258886

Chief Investigator & Study Management: [name] Co-investigators: [name] and [name]

For general queries, supply of study documentation, and collection of data, please contact: Chief investigator: [name] Address: [name] [contact] E-mail: [contact]

CLINICAL QUERIES

Clinical queries should be directed to [name] who will direct the query to the appropriate person.

SPONSOR

Imperial College London acts as the main research Sponsor for the Chief Investigator (CI). For further information regarding the sponsorship conditions, please contact:

[name], Research Governance Manager [name] [contact] E-mail: [contact]

FUNDER

The CI is funded through a Clinical Research Fellowship at Imperial College London and is not receiving any monetary compensation for the work.

This protocol describes a pre-post mixed methods pilot study assessing the impact of a mobile learning resource on the ability of clinicians to break bad news.

Every care was taken in its drafting, but corrections or amendments may be necessary. This protocol will be circulated to investigators in the study. Problems relating to this study should be referred, in the first instance, to the Cl.

This study will adhere to the principles outlined in the NHS Research Governance Framework for Health and Social Care (2nd edition). It will be conducted in compliance with the protocol, the Data Protection Act and other regulatory requirements as appropriate.

STUDY SUMMARY

Title	Mobile learning resources as a tool for improving clinician's ability to break bad news: A pre-post mixed methods pilot study.	
Design	All participants granted access to a breaking bad news mobile learning resource (VitalTips). Baseline and post-intervention questionnaires, pre- and post-intervention simulated patient encounters, and post-intervention semi-structured interviews.	
Objective	To assess if a breaking bad news mobile learning resource can improve the ability of clinicians to break bad news.	

1. INTRODUCTION

1.1 BACKGROUND

Open and honest communication is paramount when aiming to provide safe, high quality care (1–4). Some conversations can be difficult, such as when breaking bad news (BBN) (5–7). Clinicians cite a number of fears when BBN (6), such as causing harm to the patient and or their relatives (8,9), but avoiding these difficult conversations may cause undue harm (1,10–13).

Effective communication is a complex two-way process (11,14), and is a teachable core skill (1,6). Communication skills training (CST) has been incorporated into health and social care professionals' training curriculums (15,16), reflecting its growing importance. However, as less than 2% of time in medical school is devoted to CST (17), there is a need and opportunity to provide adequate and appropriate training. Most CST courses are delivered face-to-face, which can be expensive, time-consuming to facilitate, and difficult to attend (17–20). As such, alternative methods of training need to be developed that are flexible, readily accessible and cost-effective (21).

The integration and use of digital technologies in education has increased rapidly in the last decade (22) and altered the way we learn and think (23). Digital learning is increasingly used in workplaces, classrooms and for continued professional development (22,24–28). Digital learning facilitates learning at your own pace and in your own time (18), and removes the constraints of the traditional classroom-based learning model (22). Having immediate access to the world wide web, social media, blogs and e-mail suits our current culture of learning (27).

A recent study reported that within a London hospital 98.9% of doctors and 95.1% of nurses owned a smartphone, and 73.5% and 64.7% owned a tablet device, respectively (29). Medical applications were owned by 78.3% doctors and 34.8% nurses, with the majority used for reference and training (29). With mobile devices becoming increasingly commonplace in healthcare (29–31), and evidence to support the use of digital learning for clinical skills acquisition (28,32,33), this medium of learning affords an avenue for CST and BBN training. However, the evidence-base is limited (4), especially when considering mobile learning as sub-set of digital learning (34,35).

1.2 RATIONALE

Digital and mobile learning is at the forefront of healthcare education, but there is little evidence of its use for breaking bad news training. This study aims to address this gap in knowledge by assessing how mobile learning resources may impact the ability of clinicians to break bad news.

1.3 HYPOTHESIS

The addition of a breaking bad news mobile learning resource to clinical practice improves the ability of junior doctors and nurses to break bad news.

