2. STUDY OBJECTIVE

To assess if a breaking bad news mobile learning resource can improve the ability of clinicians to break bad news.

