3. STUDY DESIGN

3.1 METHODOLOGY & DESIGN

The study objective will be investigated through a pre-post mixed methods pilot study (see figure 1).

Potential participants will be sent invitation e-mails (appendix 1A and 1B). Once potential participants have read the participant information sheet (PIS) (appendix 2) and given consent (appendix 3), they will be asked to complete a baseline questionnaire (appendix 4) to understand their demographics, their previous exposure to breaking bad news (through formal or informal training) and their engagement with digital resources.

Following consent, participants will be asked to complete a baseline simulated patient encounter (SPE) with a simulated patient (SP) (role-played by a professional actor/patient) to assess their baseline ability to break bad news. Participants will be given a task sheet (appendix 6A) with a brief history of the SP and what news they need to deliver. The details and history of the SP will be documented on a character sheet (appendix 7A) for the professional actor/patient to refer to. The SPE will last 15 minutes and it will be video-recorded. The SPEs will be evaluated against a validated mark sheet (36) (appendix 8) completed by the SP, the CI (immediately following the SPE) and an independent assessor (by watching the video footage).

Following the pre-intervention SPE, access to the mobile learning resource will be granted. The mobile learning resource is the freely available VitalTips mobile application, provided by VitalTalk. The participants will be expected to spend at least three hours using the VitalTips app, without this time impacting on their clinical and academic commitments. As the in-application metrics will not be available to the researchers, participants will be asked to self-report their engagement with the resource in the post-intervention questionnaire (appendix 5).

Four to six weeks later, all participants will be asked to complete a second videoed SPE, which will be marked as described above. The participants will also be asked to complete a post-intervention questionnaire to gauge the impact on their clinical practice and their engagement with the mobile resources. Each participant will act as their own control when comparing the baseline and post-intervention SPE scores and questionnaire responses.

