7. STATISTICS & DATA ANALYSIS

7.1 SAMPLE SIZE

Due to the exploratory nature of this educational pilot study, the sample size will be relatively small, especially as all participants will be given the intervention and there are no comparator groups. Considering that there are two professional groups involved (doctors and nurses) a sample of ten participants from each (20 in total) should be sufficient to answer the research question and allow for thematic analysis of the post-intervention interview transcripts.

Schildmann et al. and similar studies either did not formally report on or had low attrition rates as their interventions were part of the participant's training (44). This makes it difficult to estimate the level of attrition in our study, especially as the intervention is not mandatory for training. However, it is estimated that attrition levels will be low as evidenced by similar studies.

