7.2 DATA ANALYSIS

Data will be analysed at Imperial College London.

The SPE will be marked by three assessors: the CI, the SP and an independent assessor. The marks are in the form of a numerical scale (appendix 8) for quantitative analysis. The scores will be recorded on an Excel spreadsheet against the participant ID. Each participant will act as their own control, with their baseline and post-intervention scores being compared. Using IBM[®] SPSS Statistics Software, a paired sample t-test will be used to statistically analyse the results (with p < 0.05 considered a statistically significant change).

The baseline and post-intervention questionnaires will be analysed by the CI using a combination of a spreadsheet for the quantitative elements (converting the Likert scale into a numerical scale), and qualitative data management software (i.e. NVivo from QRS International) for the white space answers.

The user's confidence in breaking bad news at baseline and post-intervention will be self-assessed on a Likert scale which will be converted to a numerical scale:

- Confidence five-point scale: Not very confident at all (= 0); not very confident (= 1); somewhat confident (= 2); very confident (= 3); extremely confident (= 4).
- Agreeability five-point scale: Strongly disagree (= 0); disagree (= 1); neutral (= 2); agree (= 3); strongly agree (= 4).

Each participant will act as their own control, with comparisons drawn from their own Likert scale ratings from baseline and post-intervention. A paired sample t-test will be used to statistically analyse the results as above.

The answers to open ended questions will be transcribed into a Word file and then uploaded onto NVivo for thematic analysis. This will be performed by the CI becoming familiar with the content of the transcriptions and then thematically coded and analysed. To counter analysis bias, a selection will be reviewed and coded by a second researcher, with any disagreement resolved through discussion. The second researcher will not have access to personal data and will only view anonymised transcripts.

The semi-structured interviews will be transcribed verbatim either by the CI or PageSix Transcription Services and analysed by the CI using NVivo (qualitative data management software). Thematic analysis will be performed by the CI by becoming familiar with the content of the transcriptions

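### The hypothesis and objective ask whether the app improves ability, but a single-arm paired test can only show that scores differ between the first and second assessments

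*Combined protocol and SAP*

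**What the plan says.** - **Hypothesis (1.3):** adding the resource to clinical practice "improves the ability of junior doctors and nurses to break bad news".
- **Objective (2, repeated in the study summary):** "To assess if a breaking bad news mobile learning resource can improve the ability of clinicians to break bad news".
- **Design (7.1):** "all participants will be given the intervention and there are no comparator groups".
- **Sample size (7.1, 15 to 20 in the study summary):** ten doctors and ten nurses, "20 in total) should be sufficient to answer the research question". No effect size, SD or power is given.
- **Comparison (3.1):** "Each participant will act as their own control when comparing the baseline and post-intervention SPE scores and questionnaire responses". Section 7.2 repeats this for the simulated encounter scores.
- **Test (7.2):** "a paired sample t-test will be used to statistically analyse the results", "with p < 0.05 considered a statistically significant change". The same test is applied to the Likert ratings.

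The title, 3.1 and 7.1 describe the study as a pre-post pilot, and 7.1 calls it exploratory. No section says that a before-after change cannot be attributed to the app.

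**The concern.** The question is causal and the analysis is not. Using participants as their own controls removes stable differences between people. It does not remove anything else that changes between the two occasions, and the documents show several such things. A significant paired test could therefore be taken as the answer to the objective when it answers only whether scores moved. Section 7.1 encourages that step by saying that the sample can answer the research question. Without a comparator, the obstacle is the design, and no sample size overcomes it.

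At stake is the conclusion drawn in the publications and thesis foreseen in section 10, and the basis on which a later controlled study would be justified.

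**Working it through.** **1. What the paired test estimates.** For each participant, D = second score − first score. The test statistic is t = mean(D) / (SD(D)/√n), on n − 1 degrees of freedom. The expected value of D is the app effect plus the sum of all other changes between the assessments. The null hypothesis tested is that this total is zero. The hypothesis in 1.3 concerns the first term alone, which one arm cannot isolate.

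**2. What the documents leave in the second term.**
- *Repeat exposure:* the same 15-minute encounter format is used twice (3.1, 3.5).
- *Scenario:* the two encounters use different cases (3.5). No counterbalancing is described, so case difficulty is tied to time point.
- *Clinical work:* four to six weeks pass (3.1), and recruitment is aimed at specialties where bad news is often broken (3.2).
- *Other training and resources:* the post-intervention questionnaire (Appendix 5) asks about both, but 7.2 makes no use of the answers.
- *Rating:* the simulated patient and the chief investigator mark at the encounter (3.5). No masking to time point is described for any assessor, and the video files carry an SPE1 or SPE2 label (3.6).

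Repeat exposure may raise scores. A harder second case would lower them and an easier one would raise them. The documents do not settle the sign of the sum.

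**3. Whether a comparator exists elsewhere in the text.** Section 3.4 (Consent) and section 3.5 mention randomisation, the Figure 1 caption mentions a quasi-randomised trial, and Appendix 5 mentions an intervention group. None of this defines a second arm, and 7.1 says that there is none.

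**4. Size, as an illustration.** The plan has no power figure to reproduce. Inputs:
- n = 20 (7.1) and n = 15 (lower end of the range in the study summary).
- α = 0.05 (7.2); two-sided is assumed, as sidedness is not stated.
- App effect set to zero.
- Drift d = mean non-app change divided by the SD of D. The values 0.2 to 0.5 are assumptions; the documents give none.

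P(significant improvement) = P(T > t₀.₉₇₅,ₙ₋₁), where T is noncentral t with n − 1 degrees of freedom and noncentrality d√n. Critical values are 2.093 (n = 20) and 2.145 (n = 15).

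Worked case: n = 20, d = 0.5 gives noncentrality 0.5 × √20 = 2.236 and probability 0.564.

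| Assumed drift d | n = 20 | n = 15 |
|---|---|---|
| 0 | 2.5% | 2.5% |
| 0.2 | 13% | 11% |
| 0.3 | 25% | 19% |
| 0.4 | 40% | 30% |
| 0.5 | 56% | 44% |

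A downward drift of the same size would, by symmetry, give the same chances of a significant worsening with no app effect, and would mask a real benefit.

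**5. Effect of a larger sample.** At n = 40 the figures for d = 0.3, 0.4 and 0.5 are 46%, 69% and 87%. More participants in one arm make the drift easier to detect, so they do not help with attribution.

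**The case against.** **The case for the plan.** The design is disclosed: the title says pre-post pilot, and 7.1 says exploratory and without comparators. Section 2 asks whether the resource can improve ability; it does not assert that it does. Only 1.3 asserts improvement, and it is labelled a hypothesis. Section 7.2 already calls p < 0.05 a significant change, not an app effect. The interviews and Appendix 5 Part D ask participants about learning and impact, so the t-test is not the only evidence. Separate scenarios limit recall of the first case. The drift values are assumed and not tied to points on the mark sheet.

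**What stands.** All of this is correct, and it lowers the severity. It does not remove the mismatch. The neutral wording in 7.2 is not carried into 1.3, 2 or the sufficiency sentence in 7.1, and no limitation is stated. Interviews give perceptions and do not replace a comparator. The percentages show how the test behaves; they do not measure bias in this study.

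**Stronger readings that the documents do not support.**
- *That the plan commits the sponsor to reporting any significant result as an app effect.* Neither 7.2 nor section 10 says so.
- *That the rival influences mostly push scores upward.* Nothing in the documents shows this, and scenario difficulty could act either way.
- *That participants practise against the marking criteria.* The mark sheet is completed by assessors, and no section says that participants see it.

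**Conclusion.** The point holds as a mismatch between the question and the test. Sections 1.3 and 2 are causal, and 7.1 claims sufficiency for that question. The planned analysis can support only a statement that scores differ between the first and second assessments. The net direction of the non-app influences is unknown.

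The range of 13% to 56% at n = 20 (11% to 44% at n = 15) rests on a zero app effect, an assumed upward drift of 0.2 to 0.5 SD of the change, a two-sided 5% test and normally distributed differences. With no drift the figure is 2.5%. Severity is minor: the study is a declared exploratory pilot, and 7.2 is already close to the right wording.

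**What to change.** 1. **1.3:** keep the causal hypothesis only as the motivation for a later controlled study.
2. **Study summary and 2:** restate the objective as estimating the change in BAS score and self-rated confidence from the first to the second assessment.
3. **7.1:** replace the sufficiency sentence with one saying that the sample serves to estimate that change and its SD, and to support the thematic analysis.
4. **7.2:** state that p < 0.05 shows a change between assessments and will not by itself be attributed to the app. Name the rival explanations: repeat exposure, different scenarios, clinical work, other training, and rating without described masking.
5. **7.2:** report the mean change with 95% CI and the SD of the change as planning estimates.
6. **Self-reported hours of use:** if change is shown by hours (Appendix 5, Part C), keep it descriptive. Hours are self-chosen and recorded in five bands among 15 to 20 people, so they are not evidence of an app effect.

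**Cost:** edits to five places in the text and a less favourable claim. No extra arm, participants or procedures are needed.

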2. STUDY OBJECTIVE

To assess if a breaking bad news mobile learning resource can improve the ability of clinicians to break bad news.

3. STUDY DESIGN

3.1 METHODOLOGY & DESIGN

The study objective will be investigated through a pre-post mixed methods pilot study (see figure 1).

Potential participants will be sent invitation e-mails (appendix 1A and 1B). Once potential participants have read the participant information sheet (PIS) (appendix 2) and given consent (appendix 3), they will be asked to complete a baseline questionnaire (appendix 4) to understand their demographics, their previous exposure to breaking bad news (through formal or informal training) and their engagement with digital resources.

Following consent, participants will be asked to complete a baseline simulated patient encounter (SPE) with a simulated patient (SP) (role-played by a professional actor/patient) to assess their baseline ability to break bad news. Participants will be given a task sheet (appendix 6A) with a brief history of the SP and what news they need to deliver. The details and history of the SP will be documented on a character sheet (appendix 7A) for the professional actor/patient to refer to. The SPE will last 15 minutes and it will be video-recorded. The SPEs will be evaluated against a validated mark sheet (36) (appendix 8) completed by the SP, the CI (immediately following the SPE) and an independent assessor (by watching the video footage).

Following the pre-intervention SPE, access to the mobile learning resource will be granted. The mobile learning resource is the freely available VitalTips mobile application, provided by VitalTalk. The participants will be expected to spend at least three hours using the VitalTips app, without this time impacting on their clinical and academic commitments. As the in-application metrics will not be available to the researchers, participants will be asked to self-report their engagement with the resource in the post-intervention questionnaire (appendix 5).

Four to six weeks later, all participants will be asked to complete a second videoed SPE, which will be marked as described above. The participants will also be asked to complete a post-intervention questionnaire to gauge the impact on their clinical practice and their engagement with the mobile resources. Each participant will act as their own control when comparing the baseline and post-intervention SPE scores and questionnaire responses.

Soon after the completion of the questionnaire, the participant will be asked to participate in a 15-30 minutes semi-structured interview with the researcher. The participant will be asked about their general impressions of the mobile learning resource, their use of the resource in and outside of the clinical environment, their perception of their ability to break bad news before and after the intervention, their perception of their performance in the SPE and any impact on their practice.

3.2 STUDY SETTING

Participants will be recruited from hospitals within two NHS trusts - Imperial College Healthcare NHS Trust and Barts Health NHS Trust, and one private health care site - Bupa Cromwell Hospital. The intention is to recruit those working across a range of specialities, where staff frequently break bad news (e.g. oncology).

The study is intended to commence in January 2019 (dependant on HRA ethical approval) with final recruitment to be at the end of June 2019, to complete the study by August 2019.

Figure 1: Outline of quasi-randomised controlled trial

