3.3 PARTICIPANTS

Participants will be junior doctors (of any specialty, pre-certificate of completion of training) and junior nurses (of any specialty, band 5 to 6), currently working and training within the NHS or a private healthcare hospital in England. All participants must be able to communicate and write in English. They must be willing to engage with a mobile learning resource as an additional task to their clinical role, ensuring their learning does not take time out of their clinical commitments. Potential participants will be excluded if they are undergraduates, completed their training or retired.

There will be no coercion or pressure to participate. There will be no monetary reward for participation. Participants may use the SPE as a work-based assessment to be completed by the CI upon request.

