4.2 INCLUSION CRITERIA

- Working and training within NHS England and Bupa Cromwell Hospital.
- Junior doctor, pre-certificate of completion of training (of any specialty).
- Junior nurse band 5 to 6 (any specialty).
- Over the age of 18.
- Able to communicate and write in English.
- Willing to engage with mobile learning resources as an additional task to their clinical role, ensuring their learning does not take time out of their clinical commitments.

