Appendix 4 Baseline questionnaire

Baseline Questionnaire 2.1 (18/03/2019)

Mobile learning resources as a tool for improving clinician's ability to break bad news: A pre-post mixed methods pilot study

(IRAS ID 258886)

Participant ID:

Thank you for taking part in this study. Please could you complete this questionnaire? It is likely to take 15 minutes to complete. Your answers will be kept confidential.

PART A

Demographics 1. What is your gender?

Male / Female / Other / Rather not say

2. Which age bracket applies to you?

18-24 years old 25-34 years old 35-44 years old 45-54 years old 55-64 years old 65+

3A. What is your role?

Doctor / Nurse

3B. How long have you worked in this role?

_____ years

Breaking bad news 4. In your role, are you involved in breaking bad news?

Yes / No

4B. If 'Yes', in what capacity?

Comment:

4C. If 'Yes', how often are you involved in breaking bad news in a week?

Comment:

Training

5A. Have you received training on breaking bad news at either the undergraduate or postgraduate level?

Yes / No

5B. If 'Yes', what training did you receive?

Comment:

Mobile devices & learning

6A. Do you own or have access to a smartphone or tablet which you use whilst at work?

Yes / No

6B. If 'Yes', do you use the smartphone or tablet at work for learning?

Yes / No

6C. If 'Yes', what features or applications on your device(s) do you use for work?

Comment:

7. Have you ever used digital learning resources for breaking bad news training?

Yes / No

Comment:

PART B

Breaking bad news competencies

Please rate your level of confidence regarding the following statements related to breaking bad news:

1. Your ability to break bad news well.

Not very confident at all Not very confident Somewhat confident Very confident Extremely confident

2. Your ability to recognise when to break bad news.

Not very confident at all Not very confident Somewhat confident Very confident Extremely confident

3. Your ability to break bad news in planned and unexpected settings.

Not very confident at all Not very confident Somewhat confident Very confident Extremely confident

4. Your ability to be empathetic, honest and sensitive when breaking bad news.

Not very confident at all Not very confident Somewhat confident Very confident Extremely confident

5. Your ability to prepare for breaking bad news (i.e. setting the environment, having sufficient information).

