Strongly disagree Disagree Neutral Agree Strongly agree

4. I am able to break bad news in my practice earlier than I would have before.

Strongly disagree Disagree Neutral Agree Strongly agree

5. I am better prepared for breaking bad news conversations.

Strongly disagree Disagree Neutral Agree Strongly agree

6. When I break bad news, I feel that I am doing something positive for the person/people I am speaking with.

Strongly disagree Disagree Neutral Agree Strongly agree

PART C (for those in the interventional group)

1. How long did you spend using the mobile learning resource in total?

<1 hour 1-2 hours 2-3 hours 3-4 hours >4 hours

2. How often did you use the mobile resource at work?

Never

Once only Once a week Once a day Multiple times a day

3. How often did you use the mobile resource outside of work?

Never Once only Once a week Once a day Multiple times a day

4A. Did you use any other mobile learning resources during the last few weeks?

Yes / No

4B. If 'Yes', could you specify which one(s) and why?

Comment:

PART D (for those in the interventional group)

Having used the mobile learning resource, please rate how you feel regarding the following statements:

1. The mobile learning resource was useful for my clinical practice.

Strongly disagree Disagree Neutral Agree Strongly agree

2. It was easy to learn about breaking bad news using the mobile learning resource.

Strongly disagree Disagree Neutral Agree Strongly agree

3. Using the mobile learning resource was time consuming, impacting negatively on the time I spend on clinical work.

Strongly disagree Disagree

Neutral Agree Strongly agree

4. The mobile learning resource did not teach me anything new.

Strongly disagree Disagree Neutral Agree Strongly agree

5. The learning from the mobile resource has not had an influence on the way I work.

Strongly disagree Disagree Neutral Agree Strongly agree

6. A mobile learning resource was a good choice of learning-tool for breaking bad news training.

Strongly disagree Disagree Neutral Agree Strongly agree

7. Would you recommend the mobile learning resource to your colleagues? Yes / No

8. Do you have any further comments about the mobile learning resource and/or how the knowledge you gained has influenced your clinical practice?

Yes / No

Comments:

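### The practice-impact ratings in the post-intervention questionnaire cannot tell no effect on practice from no opportunity to apply the learning

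*Combined protocol and SAP*

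**What the plan says.** **Who is recruited.** Section 3.2 states an aim: "The intention is to recruit those working across a range of specialities, where staff frequently break bad news (e.g. oncology". Section 3.3 defines participants as "junior doctors (of any specialty, pre-certificate of completion of training) and junior nurses (of any specialty, band 5 to 6". Section 4.2 repeats this, for example "Junior nurse band 5 to 6 (any specialty". None of the six inclusion criteria or three exclusion criteria mentions involvement in breaking bad news.

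**What is asked at baseline.** Appendix 4, Part A, item 4 asks "In your role, are you involved in breaking bad news", with Yes or No as answers. Those who answer Yes are then asked "how often are you involved in breaking bad news in a week". Section 7.2 gives neither answer a role in the analysis.

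**What is asked afterwards.** Section 3.1 plans a "post-intervention questionnaire to gauge the impact on their clinical practice and their engagement with the mobile resources", four to six weeks after the app becomes available. Appendix 5 asks about time spent on the app and how often it was used in and outside work (Part C). It does not ask whether the participant broke bad news in that period. Part B item 6 asks how the respondent feels when breaking bad news. Part D item 1 asks whether the app was useful for clinical practice. Part D item 5 reads "The learning from the mobile resource has not had an influence on the way I work". Each has five options from strong disagreement to strong agreement.

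**How it is scored.** Section 7.2 codes agreement 0 to 4, with neutral at 2. It has no code for an item that does not apply and no rule for a blank.

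**The concern.** A rating of impact on practice is informative only if there was practice to affect. The criteria allow someone who answers No to baseline item 4 to enrol. Even a junior clinician who is usually involved may meet no such conversation in four to six weeks, so the baseline frequency answer cannot stand in for what happened during follow-up.

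A participant with no occasion has no way to say so on the three items. Neutral, disagreement, or agreement that the app had no influence are all plausible replies. Each looks the same as the reply of someone who had several such conversations and found the app made no difference. What is lost is the reason behind the rating. That reason matters for a questionnaire meant to gauge impact on practice, and in a pilot it would also be useful to learn how often participants could apply the training.

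**Working it through.** The only planning figure is the sample size in Section 7.1: 10 doctors + 10 nurses = 20. It rests on judgement, with no effect size, SD or power behind it, and this point does not depend on it. The check is mainly of which items need a real occasion.

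| Measure | Needs a real conversation during follow-up? | Baseline pair? |
|---|---|---|
| Simulated encounter score (Appendix 8) | No | Yes |
| 13 confidence items (Appendix 4 Part B; Appendix 5 Part A) | No | Yes |
| Appendix 5 Part B item 4 | No, it asks about ability | No |
| Appendix 5 Part B item 6 | Presupposes that the respondent breaks bad news, though not tied to the window | No |
| Appendix 5 Part D items 1 and 5 | Can be answered without one, but the meaning then changes | No |

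Part B item 4, "I am able to break bad news in my practice earlier than I would have before", is left out of the point because a statement of ability can be rated without an occasion. Three items remain.

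**Illustration of size.** The documents give no share without opportunity, so the values here are assumptions. Take n = 20, a mean of 3 (agree) on a positively worded item among those with an occasion, and a share q without one who all give the rating r. Then:

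item mean = 3 × (1 − q) + r × q

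| Without an occasion | r = 2 (neutral) | r = 1 (disagree) |
|---|---|---|
| 0 of 20 | 3.00 | 3.00 |
| 2 of 20 (10%) | 2.90 | 2.80 |
| 5 of 20 (25%) | 2.75 | 2.50 |
| 10 of 20 (50%) | 2.50 | 2.00 |

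For example, 0.75 × 3 + 0.25 × 2 = 2.75, and 0.75 × 3 + 0.25 × 1 = 2.50. Each such person moves the mean by 1/20 = 0.05 (neutral) or 2/20 = 0.10 (disagree).

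A mean of 2.50 can come from 5 people without an occasion who disagree, from 10 who tick neutral, or from 20 people who all had occasions and were lukewarm. Nothing collected in the questionnaire separates the three.

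Part D item 5 is worded negatively, so it moves the other way. If those with an occasion average 1 and 5 of 20 without one tick agree (3), the mean is 0.75 × 1 + 0.25 × 3 = 1.50 instead of 1.00. Section 7.2 states no reverse scoring, so a high code on this item means less influence.

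**The case against.** The case against is strong on scope.

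- **No scoring rule turns lack of opportunity into lack of effect.** A reader might infer one from the missing option. Section 7.2 does not contain one: neutral is the midpoint, no forced response is stated, and an item can be left blank. This stands.
- **No summary score is at risk.** Parts B and D are asked only after the intervention, so the paired t-test in Section 7.2 cannot apply to them, and the plan defines no mean or pooled score for them. This stands. The means above only illustrate what the 0 to 4 codes would show.
- **The items can be answered truthfully.** Someone with no occasion who agrees that the app did not influence their work is correct. This stands, but the reason for the answer is still not recorded.
- **The hypothesis is about ability.** Sections 1.3 and 2 concern the ability to break bad news, which the encounters and confidence items measure without any real conversation. This stands and limits the point to a secondary purpose of the questionnaire.
- **Other sources may help.** The interview guide (Appendix 9) asks about impact on practice and about using the app before real conversations. Part D item 8 invites a comment, and baseline items 4 to 4C record usual involvement. These may reveal lack of opportunity qualitatively, but none counts occasions during follow-up for every participant.

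A reader might also infer that Sections 3.2 and 4.2 contradict each other, or that entry should be restricted to those involved in breaking bad news. Section 3.2 states an intention, and recruiting preferentially within wider criteria is consistent with it. Baseline item 4 is answered after consent, Section 4.1 provides for no pre-registration evaluation, and the item records any involvement, not frequent involvement. Using it as a criterion would therefore need a new step and would still not deliver the stated aim.

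**Conclusion.** The point holds for three descriptive items: Appendix 5 Part B item 6 and Part D items 1 and 5. With open eligibility, a four-to-six-week window, no question on occasions and no no-opportunity answer, their ratings cannot distinguish an unchanged practice from an absence of occasions. Part B item 6 is the least tied to the window, but it still presupposes that the respondent breaks bad news.

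The size is unknown because the documents give no share without opportunity. Under the assumptions above, 2 to 10 such people among 20 would lower a positively worded item by 0.10 to 0.50 points if they tick neutral, or by 0.20 to 1.00 if they disagree.

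It would go too far to say that the plan counts lack of opportunity as failure of the app, or that the study's test of ability is compromised. The encounter scores and the 13 paired confidence items are untouched. This is a cheap improvement to the instrument.

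**What to change.** 1. In Appendix 5 add: *About how many times have you broken bad news, or been present when it was broken, since the first encounter?* Make clear that this means real conversations and not the simulated ones.
2. Add the option *No opportunity since the first encounter* to Part B item 6 and Part D items 1 and 5, and keep it outside the 0 to 4 coding in Section 7.2.
3. In Section 7.2, state that these three items will be reported for all participants, with the new option as its own category, and separately for those with at least one conversation, giving the number without one.
4. Leave eligibility unchanged.

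The cost is one extra question, one response option on three items, and a smaller denominator for the exposed-only summary of those items.
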